A cut-off date for randomization was added to provide further specification of the subject population from CNTO136ARA3002 from which samples will be collected.

Sections Affected	Original Content	Amended/New Content

Time and Events Schedule (Table 1)
	
i. Pharm serum samples (sirukumab concentration and antibodies to sirukumab) will be collected from subjects who had pharm serum samples collected at earlier time points in study CNTO136ARA3002 (approximately 750 randomized subjects in CNTO136ARA3002) and from all subjects enrolled after participating in study CNTO136ARA3003.
	
i. Pharm serum samples (sirukumab concentration and antibodies to sirukumab) will be collected from subjects who had pharm serum samples collected at earlier time points in study CNTO136ARA3002 (approximately 750 randomized subjects randomized in CNTO136ARA3002 before 18 November 2013) and from all subjects enrolled after participating in study CNTO136ARA3003.

Time and Events Schedule (Table 2)
	
c. Pharm serum samples (sirukumab concentration and antibodies to sirukumab) will be collected at the final safety and efficacy follow up visit only from those subjects who had pharm serum samples collected at earlier time points in study CNTO136ARA3002 (approximately 750 randomized subjects in CNTO136ARA3002) and from all subjects enrolled after participating in study CNTO136ARA3003.
	
c. Pharm serum samples (sirukumab concentration and antibodies to sirukumab) will be collected at the final safety and efficacy follow up visit only from those subjects who had pharm serum samples collected at earlier time points in study CNTO136ARA3002 (approximately 750 randomized subjects randomized in CNTO136ARA3002 before 18 November 2013) and from all subjects enrolled after participating in study CNTO136ARA3003.

CNTO 136 (sirukumab): Clinical Protocol CNTO136ARA3004 – Amendment 3

6. A clarification regarding joint assessors was made.

The joint assessors are not required to be independent.

Sections Affected	Original Content	Amended/New Content
9.2.1.1 Joint Assessments (Joint Assessor paragraph 3)	The Sponsor will provide training for each site's designated IJA prior to the [Week 0 visit] of the first subject at each site. A back-up IJA must complete training before performing a joint assessment for a subject's study visit.	The Sponsor will provide training for each site's designated IJA joint assessor prior to the [Week 0 visit] of the first subject at each site. A back-up IJA joint assessor must complete training before performing a joint assessment for a subject's study visit.

7. A specification was made regarding how long subjects are required to be monitored for allergic and injection site reactions throughout the study.

Clarifying language was added to the Safety Evaluations to specify that subjects only need to undergo monitoring for symptoms of allergic reactions and injection site reactions at least until the study becomes open-label.

Sections Affected	Original Content	Amended/New Content
9.8 Safety Evaluations (Allergic Reactions)	All subjects will be observed carefully for symptoms of allergic reactions for at least 30 minutes after the SC injection of study agent at the study site.	All subjects will be observed carefully for symptoms of allergic reactions for at least 30 minutes after the SC injection of study agent at the study site at least until the study becomes open-label.
9.8 Safety Evaluations (Injection Site Reactions)	An injection site reaction is any unfavorable or unintended sign that occurs at the study agent injection site. All subjects must be carefully observed for symptoms of an injection site reaction. Subjects will be observed for at least 30 minutes after the SC injection of study agent for symptoms of an injection-site reaction.	An injection site reaction is any unfavorable or unintended sign that occurs at the study agent injection site. All subjects must be carefully observed for symptoms of an injection site reaction. Subjects will be observed for at least 30 minutes after the SC injection of study agent for symptoms of an injection-site reaction at least until the study becomes open-label.

CNTO 136 (sirukumab): Clinical Protocol CNTO136ARA3004 – Amendment 3

8. A criterion was added to the Subject Completion / Withdrawal criteria for completeness.

A criterion for discontinuation of study treatment was added to address the potential future approval of sirukumab in the subject's country of residence. This is already mentioned earlier in the document, but is being added to this list for completeness.

Sections Affected	Original Content	Amended/New Content
10.2 Discontinuation of Treatment	None	16. If sirukumab becomes approved in the subject's country of residence, it may no longer be offered by the Sponsor in CNTO136ARA3004. In this case, study agent administrations will be discontinued after 52 weeks of treatment for subjects who enrolled after completing participation in study CNTO136ARA3002, and after 104 weeks of treatment for subjects who enrolled after completing participation in CNTO136ARA3003. At that point the subject will have the opportunity to discuss treatment options with their treating physician.

9. The list of anticipated events was updated and language was moved to an attachment at the end of the protocol.

Language was added to include synovitis in the list of anticipated events, which was moved from section 12.3.2 to a new attachment (Attachment 2) at the end of the protocol. A reference to this attachment was included in section 12.3.1 (All Adverse Events).

Sections Affected	Original Content	Amended/New Content
12.3.1 All Adverse Events (paragraph 2)	All events that meet the definition of a SAE will be reported as SAEs, regardless of whether they are protocol-specific assessments. All adverse events, regardless of seriousness, severity, or presumed relationship to study therapy, must be recorded using medical terminology in the source document and the CRF. Whenever possible, diagnoses should be given when signs and symptoms are due to a common etiology (eg, cough, runny nose, sneezing, sore throat, and head congestion should be reported as "upper respiratory infection"). Investigators must record in the CRF their opinion concerning the relationship of the adverse event to study therapy. All measures required for adverse event management must be recorded in the source document and reported according to Sponsor instructions.	All events that meet the definition of a SAE will be reported as SAEs, regardless of whether they are protocol-specific assessments. Anticipated events will be recorded and reported as described in Attachment 2. All adverse events, regardless of seriousness, severity, or presumed relationship to study therapy, must be recorded using medical terminology in the source document and the CRF. Whenever possible, diagnoses should be given when signs and symptoms are due to a common etiology (eg, cough, runny nose, sneezing, sore throat, and head congestion should be reported as "upper respiratory infection"). Investigators must record in the CRF their opinion concerning the relationship of the adverse event to study therapy. All measures required for adverse event management must be recorded in the source document and reported according to Sponsor instructions.


12.3.2 Serious Adverse Events (paragraphs 7, 8)
	
SAEs related to the disease under study will be collected per protocol but will not be unblinded and expedited if they fall into the following categories:
 
 • Exacerbations of RA • Worsening joint pain or swelling due to RA 
These events will be reviewed periodically at the time of database locks in an unblinded fashion, if unblinded data is available. In addition, the DMC will review unblinded data during the blinded portions of the study (Section 11.10). If the review finds an association with the use of the drug to be a reasonable possibility, the assessment and all single cases not yet reported will be sent to FDA in an expedited manner.
	
SAEs related to the disease under study will be collected per protocol but will not be unblinded and expedited if they fall into the following categories:
 
 • Exacerbations of RA • Worsening joint pain or swelling due to RA 
These events will be reviewed periodically at the time of database locks in an unblinded fashion, if unblinded data is available. In addition, the DMC will review unblinded data during the blinded portions of the study (Section 11.10). If the review finds an association with the use of the drug to be a reasonable possibility, the assessment and all single cases not yet reported will be sent to FDA in an expedited manner.


Attachment 2: Anticipated Events
	
None
	
An anticipated event is an adverse event (serious or non-serious) that commonly occurs as a consequence of the underlying disease or condition under investigation (disease related) or background regimen. For the purposes of this study the following events will be considered anticipated events:
 
 • Exacerbations of rheumatoid arthritis (RA) • Worsening joint pain or swelling due to RA • Synovitis 
Reporting of Anticipated Events These events will be captured on the CRF and in the database, and will be reported to the sponsor as described in Section 12.3.1, All Adverse Events. Any event that meets serious adverse event criteria will be reported to the sponsor within the appropriate timeline as described in Section 12.3.2, Serious Adverse Events. These anticipated events are exempt from expedited reporting as individual single cases to Health Authorities. However, if based on an aggregate review, it is determined that an anticipated event is possibly related to study drug, the sponsor will report these events in an expedited manner.

		
Anticipated Event Review Committee (ARC) An Anticipated Event Review Committee (ARC) will be established to perform reviews of pre-specified anticipated events at an aggregate level. The ARC is a safety committee within the sponsor’s organization that is independent of the sponsor’s study team. The ARC will meet to aid in the recommendation to the sponsor’s study team as to whether there is a reasonable possibility that an anticipated event is related to the study drug.
 
Statistical Analysis Details of statistical analysis of anticipated events, including the frequency of review and threshold to trigger an aggregate analysis of anticipated events will be provided in a separate Anticipated Events Safety Monitoring Plan (ASMP).

--	--	--

10. Language for consent regarding pregnancy was updated for greater specification.

Language was added regarding consent guidelines for male and female subjects involved in pregnancy during the study.

Sections Affected	Original Content	Amended/New Content

12.3.3 Pregnancy (paragraph 3)
	
Follow-up information regarding the outcome of the pregnancy and any postnatal sequelae in the infant will be required.
	
Follow-up information regarding the outcome of the pregnancy and any postnatal sequelae in the infant will be required after subject’s consent has been obtained.
 
 • For women: The study doctor will ask for your permission to stay in contact with you throughout the length of the pregnancy. • For men: The study doctor will ask for your permission and your partner’s to stay in contact with your partner throughout the pregnancy.

11. Updates were made to the Study Specific Materials.

As this is an outsourced study, “Site Investigational Product Binder” is not being used. “Binder” was replaced with “Procedures Manual” for consistency with other related Phase 3 studies. Updates were also made for some of the names of the Study Specific Materials that are provided to the investigator.

Sections Affected	Original Content	Amended/New Content
14.4 Preparation, Handling, and Storage (paragraphs 3 and 4)	Study agent should be administered according to the instructions provided in the Site Investigational Product Binder. Subjects who are able and who have been appropriately trained in the self-administration of study agent may self-administer study agent at home in accordance with Section 6.5. Study personnel will instruct subjects on how to transport, store and administer medication for at-home use as indicated for this protocol. Details will be provided in the Site Investigational Product Binder.	Study agent should be administered according to the instructions provided in the Site Investigational Product Binder Procedures Manual . Subjects who are able and who have been appropriately trained in the self-administration of study agent may self-administer study agent at home in accordance with Section 6.5. Study personnel will instruct subjects on how to transport, store and administer medication for at-home use as indicated for this protocol. Details will be provided in the Site Investigational Product Binder Procedures Manual .
14.5 Drug Accountability (paragraph 2)	Upon termination of the study or at the request of the Sponsor or its designee, the investigator must return all unused study agent to the Sponsor or its designee or if approved by the Sponsor, unused study agent can be destroyed directly at the site or locally by an approved destruction unit as described in the Site Investigational Product Binder.	Upon termination of the study or at the request of the Sponsor or its designee, the investigator must return all unused study agent to the Sponsor or its designee or if approved by the Sponsor, unused study agent can be destroyed directly at the site or locally by an approved destruction unit as described in the Site Investigational Product Binder Procedures Manual .
15 Study Specific Materials	The investigator will be provided with the following: 
 Investigator Brochure Site Investigational Product Binder Central Laboratory Manual PRO Questionnaires MTX Toxicity Guidelines (Appendix C) IVRS/IWRS Manual Electronic Data Capture (eDC) Manual 	The investigator will be provided with the following: 
 Investigator Brochure Site Investigational Product Binder Procedures Manual Central Laboratory Manual PRO Questionnaires ePRO Device and Manual MTX Toxicity Guidelines (Appendix C) IVRS/IWRS Manual User Guides and Worksheets Electronic Data Capture (eDC) Manual

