- f. Urine pregnancy testing during the study for women of childbearing potential only. Additional pregnancy tests may be performed, as determined necessary by the investigator or required by local regulation, to establish the absence of pregnancy at any time during the subject's participation in the study.
- g. RA assessments include the following: patient pain assessment; patient global assessment of disease activity, physician global assessment of disease activity, Health Assessment Questionnaire-Disability Index, and duration of morning stiffness.
- h. At selected sites, the MPSQ will be administered as an optional paper questionnaire to subjects who consent to participate after implementation of Amendment 3 at the study site.
- i. Pharm serum samples (sirukumab concentration and antibodies to sirukumab) will be collected from subjects who had pharm serum samples collected at earlier time points in study CNTO136ARA3002 (approximately 750 subjects randomized in CNTO136ARA3002 before 18 November 2013) and from all subjects enrolled after participating in study CNTO136ARA3003.
- j. On days of study agent administration, Pharm serum samples (sirukumab concentration and antibodies to sirukumab) must be collected prior to administration. Blood collected from one venipuncture will be divided into 3 serum aliquots (1 each sirukumab concentration, antibodies to sirukumab and a backup sample). Refer to the Central Laboratory Manual for more detailed instructions.
- k. Pharm serum samples (sirukumab concentration and antibodies to sirukumab) will be collected only from those subjects who enrolled after participating in study CNTO136ARA3003.
- l. An optional pharmacogenetics blood sample will be collected from those subjects who sign a separate consent form (where local regulations permit).

CNTO 136 (sirukumab): Clinical Protocol CNTO136ARA3004 – Amendment 3

Table 2: Times and Events in Safety and Efficacy Follow-up After Last Study Agent Injection or after Discontinuation of Study Agent				
	Week 4	Week 8	Week 12	Week 16/Final Safety and Efficacy Follow-up Visit
Study Procedure ^{a,b}				
Safety Assessments				
Blood pressure	X	X	X	X
Efficacy Assessments				
Patient pain assessment		X		X
Patient global assessment of disease		X		X
Physician global assessment of disease		X		X
Clinical Laboratory Assessments				
Hematology panel		X		X
Chemistry panel		X		X
Lipid panel (fasting)		X		X
CRP		X		X
Pharmacokinetics/ Immunogenicity				

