9.2.2.2.1 Disease Activity Index Score 28 Using CRP

The Disease Activity Index Score 28 using CRP [DAS28 (CRP)] is a derived score combining tender joints (28 joints), swollen joints (28 joints), CRP, and Patient's Global Assessment of Disease Activity (GH).⁴⁵ The DAS28 (CRP) is a continuous parameter and is defined as follows:

$$\text{DAS28 (CRP)} = 0.56 \times \text{SQRT}(\text{TEN28}) + 0.28 \times \text{SQRT}(\text{SW28}) + 0.36 \times \ln(\text{CRP} + 1) + 0.014 \times \text{GH} + 0.96$$
 where:

- The set of 28 joint count is based on evaluation of the shoulder, elbow, wrist, MCP1, MCP2, MCP3, MCP4, MCP5, PIP1, PIP2, PIP3, PIP4, PIP5 joints of both the upper right extremity and the upper left extremity as well as the knee joints of lower right and lower left extremities.
- TEN28 is 28 joint count for tenderness.
- SQRT (TEN28) is square root of TEN28.

CNTO 136 (sirukumab): Clinical Protocol CNTO136ARA3004 – Amendment 3

- SW28 is 28 joint count for swelling.
- SQRT (SW28) is square root of SW28
- Ln (CRP+1) is natural logarithm of (CRP value [mg/L] + 1).
- GH is Patient’s Global Assessment of Disease Activity on VAS.

9.2.2.2.1.1 DAS28 (CRP) Response

- DAS28 (CRP) response is defined in [Table 3](#).⁴⁵

Table 3: DAS28 (CRP) response criteria			
DAS28 (CRP) at the visit	Improvement from Baseline		
	> 1.2	> 0.6 – 1.2	≤ 0.6
• ≤ 3.2	• Good response	• Moderate response	• No response
• > 3.2 – 5.1	• Moderate response	• Moderate response	• No response
• > 5.1	• Moderate response	• No response	• No response

9.2.2.2.1.2 DAS28 (CRP) Remission

DAS28 (CRP) remission is defined as a DAS28 (CRP) value of < 2.6 at a visit.

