9.2.2.3 Simplified Disease Activity Index Score

The Simplified Disease Activity Index (SDAI) score is a derived score combining tender joints (28 joints), swollen joints (28 joints), GH, Physician’s global assessments of disease activity (PGH), and CRP.²

SDAI is defined as follows:

SDAI = TEN28 + SW28 + GH + PGH + CRP (mg/dL) where:

- TEN28 and SW28 were defined the same as in Section [9.2.2.2.1](#)
- GH is Patient’s Global Assessment of Disease Activity on VAS.
- PGH is Physician’s Global Assessment of Disease Activity on VAS.

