9.3.2 Pharmacokinetics

9.3.2.1 Serum Collection and Handling

Blood samples for the measurement of serum sirukumab concentrations will be collected at visits as shown in the Time and Events Schedules ([Table 1](#) and [Table 2](#)). For subjects who had serum samples collected at earlier time points in study CNTO136ARA3002 (approximately 750 randomized subjects in CNTO136ARA3002) and all subjects who enrolled after participating in study CNTO136ARA3003, serum samples will be collected at Weeks 2, 4, 16, 28, 52, 104, 156 and the final safety and efficacy follow-up visit ([Table 1](#) and [Table 2](#)). One additional sample will be collected at Week 208 for subjects who enrolled after participating in study CNTO136ARA3003.

The exact dates and times of blood sampling must be recorded on the laboratory requisition form. Note that if the subject is to receive an administration of study agent at that visit, blood samples will be collected prior to study agent administration.

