11.2 Efficacy and Safety Analyses

Baseline value in efficacy and safety is defined as the baseline value of study CNTO136ARA3002 or CNTO136ARA3003. No missing data imputation will be used.

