
9.7 Health Economics Evaluations
	
Health economics evaluations on employment status, impact of disease on daily productivity, and time lost from work will be collected at Weeks 28, 52, 76, 104, 128, 156, and 208. The impact of disease on patients’ daily work productivity will be measured using a VAS. The scale ranges from “not at all affected” to “affected very much”.
	
Health economics evaluations on employment status, impact of disease on daily productivity, and time lost from work will be collected. The impact of disease on patients’ daily work productivity will be measured using a VAS. The scale ranges from “not at all affected” to “affected very much”.

10.3 Withdrawal from the Study
	
If a subject discontinues study agent administration before the end of the study, follow-up assessments should be obtained as per the Time and Events Schedule described in Table 2. For details, see Section 10.3.
	
If a subject discontinues study agent administration before the end of the study, follow-up assessments should be obtained as per the Time and Events Schedule described in Table 2.

11 Statistical Methods Paragraph 3
	
Since the treatment groups are not randomly assigned in this study, no formal hypothesis testing is planned. The efficacy, safety, and PK/PD/immunogenicity analyses will be performed separately for subjects who complete each study of CNTO136ARA3002 and CNTO136ARA3003. The analyses will include all subjects enrolled in this study by study and by treatment group above.
	
Since the treatment groups are not randomly assigned in this study, no formal hypothesis testing is planned. The efficacy, safety, and PK/PD/immunogenicity analyses will be performed separately for subjects who complete studies CNTO136ARA3002 and CNTO136ARA3003. The analyses will include all subjects enrolled by study and by treatment group above.

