---	--	--

2. Efficacy assessments at Week 180 have been added.

Efficacy assessments (joint assessment, RA assessments, SF-36, WLQ, and health economics) have been added at Week 180.

Sections Affected	Original Content	Amended/New Content
Table 1 Times and Events in Long-term Extension	None	Xs noted for: 
 • Joint assessment • RA assessments • SF-36 • WLQ • Health economics

3. The guidelines for the discontinuation of treatment have been revised.

Per DMC recommendation, GI perforation and acute diverticulitis have been added to the list of conditions that would result in the permanent discontinuation of study agent administrations.

Sections Affected	Original Content	Amended/New Content
10.2 Discontinuation of Treatment	None	14. Acute diverticulitis requiring antibiotic treatment 15. Gastrointestinal perforation

CNTO 136 (sirukumab): Clinical Protocol CNTO136ARA3004 – Amendment 3

4. Clarification on subject study card content.

The subject's name and date of birth are not included on the study card.

Sections Affected	Original Content	Amended/New Content
12.3.1 All Adverse Events Paragraph 4	Subjects (or their designees, if appropriate) must be provided with a "study card" indicating the following: 
 • Subject's name • Subject number • Subject's date of birth • Study site number • Investigator's name and 24-hour contact information • Statement that the subject is participating in a clinical trial. 	Subjects (or their designees, if appropriate) must be provided with a "study card" indicating the following: 
 • Subject number • Study site number • Study number • Sponsor's emergency contact name and 24-hour telephone number (for medical staff only) • Investigator's name and contact information • Statement in the local language(s) that the subject is participating in a clinical trial.

5. Prohibited medications have been revised.

Additions have been made to the list of prohibited medications.

Sections Affected	Original Content	Amended/New Content
8.2 Prohibited Medications	None	
 • Tofacitinib (XELJANZ®) • Any other biologic therapy for the treatment of RA

6. The time frame for reporting all initial PQCs has been revised.

A clarification on the time frame for the reporting all initial PQCs has been revised.

Sections Affected	Original Content	Amended/New Content

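### CRP is not scheduled at Week 180, so DAS28 (CRP), SDAI and both ACR/EULAR remission endpoints cannot be derived at that efficacy visit

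*Protocol*

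**What the plan says.** The Amendment 2 log (Attachment 1, item 2) states that "Efficacy assessments (joint assessment, RA assessments, SF-36, WLQ, and health economics) have been added at Week 180". Table 1 footnote g defines the middle item: "RA assessments include the following: patient pain assessment; patient global assessment of disease activity, physician global assessment of disease activity", followed by HAQ-DI and morning stiffness. CRP is not in that list. It has its own row under Clinical Laboratory Assessments in Table 1, and that row has no mark at Week 180.

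Several endpoints need CRP at the visit:

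- By Section 9.2.2.2.1, DAS28 (CRP) "is a derived score combining tender joints (28 joints), swollen joints (28 joints), CRP" and the patient's global assessment. For remission, the protocol says "DAS28 (CRP) remission is defined as a DAS28 (CRP) value of < 2.6 at a visit".
- Section 9.2.2.3 gives "SDAI = TEN28 + SW28 + GH + PGH + CRP (mg/dL) where", and SDAI-based remission (Section 9.2.2.5.1) is a cut-off of 3.3 on that score.
- Boolean remission (Section 9.2.2.5.2) requires four criteria at one visit, including CRP of at most 1 mg/dL.
- ACR responses (Section 9.2.2.1) use CRP as one of five supporting components.

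Section 11.2.3 plans to tabulate all of these by treatment group across visits to the end of the study. On missing values, Section 11.2 says "No missing data imputation will be used".

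**The concern.** The clinical half of the efficacy assessment was extended to Week 180 and the laboratory half was not. A site that follows Table 1 exactly will collect joint counts, global assessments, pain and HAQ-DI at Week 180 and still be unable to form the composite scores those items feed. The over-time tables would then have an empty Week 180 column for the main disease-activity and remission measures, or one filled by a rule the protocol does not contain. The loss falls late in treatment, where efficacy visits are fewest.

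**Working it through.** No test, power or sample-size figure is involved, so the check compares the schedule with the endpoint definitions.

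**1. CRP weeks.** Table 1 has 19 visit columns: 0, 2, 4, 16, 28, 40, 52, 64, 76, 88, 104, 116, 128, 140, 156, 168, 180, 192, 208. The CRP marks fall in columns 5, 7, 9, 11, 13, 15 and 19, which are Weeks 28, 52, 76, 104, 128, 156 and 208. Column 17 (Week 180) is blank. The lipid row has the same weeks plus 180. Hematology and chemistry are marked at every visit from Week 16 to Week 208.

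**2. Is the blank real?** The sirukumab-concentration row in the same part of the table reads as Weeks 2, 4, 16, 28, 52, 104, 156 and 208. Section 9.3.2.1 says "serum samples will be collected at Weeks 2, 4, 16, 28, 52, 104, 156 and the final safety and efficacy follow-up visit", plus Week 208 for CNTO136ARA3003 subjects, which agrees. The antibody row (16, 28, 52, 104, 156, 208) agrees with Section 9.3.3. The columns are therefore aligned there. As a historical cross-check only, superseded text in the Amendment 1 log had health economics data on "time lost from work will be collected at Weeks 28, 52, 76, 104, 128, 156, and 208", which is exactly the present CRP set. That fits CRP having been left behind when Week 180 was added.

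**3. Difference.** Efficacy weeks after Amendment 2 are {28, 52, 76, 104, 128, 156, 180, 208}. Subtracting the CRP weeks leaves {180}.

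**4. Other sources of CRP at Week 180.** It is not in the RA assessments (footnote g) or the Section 9.8 chemistry panel. The PK, antibody and pharmacodynamic serum rows have no Week 180 draw. An earlier value cannot be carried forward under Section 11.2.

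**5. Effect on the 14 endpoints of Section 11.2.3.**

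| Endpoints | Needs CRP at the visit | At Week 180 |
|---|---|---|
| 1–3: ACR 20/50/70 | one of five components | partly indeterminate |
| 4–6: DAS28 response, remission, change | yes | not derivable as defined |
| 7–8: SDAI-based and Boolean remission | yes | not derivable as defined |
| 9: SDAI change | yes | not derivable |
| 10–14: CDAI change, HAQ-DI change and response, SF-36, morning stiffness | no | derivable |

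Endpoints 4 to 9 are lost: 6 of 14.

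**6. ACR.** Suppose both joint-count criteria are met and k of the four non-CRP components reach the threshold, with three of five needed. For k ≤ 1 the total is at most 2, so the subject is a non-responder. For k ≥ 3 the subject is a responder. For k = 2 the total is 2 or 3, so the response is unknown.

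**7. Size of the missing term.** The documents give no CRP distribution, so a range of 0 to 50 mg/L is assumed. The DAS28 term is 0.36 × ln(CRP + 1), and SDAI adds CRP in mg/dL (mg/L ÷ 10).

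| CRP (mg/L) | DAS28 term | SDAI term |
|---|---|---|
| 0 | 0.00 | 0.0 |
| 5 | 0.65 | 0.5 |
| 10 | 0.86 | 1.0 |
| 20 | 1.10 | 2.0 |
| 50 | 1.42 | 5.0 |

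Against remission cut-offs of 2.6 and 3.3, the missing term is too large to ignore.

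**8. Gap in time.** The on-treatment visits with joint counts after Week 156 are Weeks 180 and 208, so 1 of 2 is lost. The interval without these endpoints is 208 − 156 = 52 weeks. With CRP at Week 180 it would be 24 weeks and then 28.

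**The case against.** The strongest reply concerns scope. CNTO136ARA3002 subjects have their last dose at Week 156, so only the CNTO136ARA3003 cohort reaches Week 180. The sponsor may also stop offering treatment to that cohort after two years where the drug is approved, so the number affected is unknown. The endpoints are other secondary and descriptive, and they remain available at Weeks 156 and 208. All of that stands and limits the importance of the point.

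Second, some binary outcomes can be settled without CRP. Failing any non-CRP Boolean criterion rules out Boolean remission. A non-CRP part above 3.3 rules out SDAI remission, and a non-CRP part of DAS28 of 2.6 or more rules out DAS28 remission. This is correct, but it identifies only non-remitters. Remission cannot be confirmed in anyone, so the planned proportions still cannot be calculated.

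Third, the evidence has limits. In the extracted text the efficacy rows of Table 1 do not line up with the week headings, so the Week 180 joint and RA marks rest on the Amendment 2 log. That log describes content added, not superseded, and gives no reason for the addition. The SAP text was not available for this check, so a rule there for a missing ACR component cannot be excluded.

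Two possible rescues fail. Section 9.8 lets the sponsor request further laboratory tests, but this schedules nothing. Table 2 has CRP at follow-up Weeks 8 and 16, but no joint counts.

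**Conclusion.** The concern holds. Followed as written, the protocol collects the clinical components at Week 180 without CRP, and endpoints 4 to 9 of Section 11.2.3 cannot be derived there as defined. ACR 20/50/70 is indeterminate for subjects who meet both joint criteria with exactly two of the four non-CRP components. The reach is one visit in one cohort, but it covers every CNTO136ARA3003 subject at that visit and half of the on-treatment visits with joint counts after Week 156. The primary safety endpoint and the major secondary laboratory endpoints are not affected. The conclusion rests on the Table 1 CRP row being complete, on the Amendment 2 additions still being in force (the Amendment 3 log shows no change to either), and on the no-imputation rule applying to composite components. It merits correction because the remedy is small and restores planned endpoints.

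**What to change.** Mark CRP at Week 180 in Table 1 and in the laboratory manual, using the venipuncture already scheduled for hematology, chemistry and fasting lipids. CRP would then be drawn at Weeks 28, 52, 76, 104, 128, 156, 180 and 208, matching the efficacy visits. The cost is one more central-laboratory assay per subject at that visit and one table cell, with no extra visit or needle-stick.

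If Week 180 samples can no longer be obtained, state in the protocol or SAP that endpoints 4 to 9 are not summarized at Week 180, and give the rule for ACR 20/50/70 when CRP is missing. CDAI, HAQ-DI, SF-36 and morning stiffness can be reported at Week 180 as planned. This alternative costs only text, but the 52-week gap remains.
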